## Abbreviations

ApoA1	Apolipoprotein A1
ApoB	Apolipoprotein B
BIA	Bioelectrical impedance analysis
BMI	Body mass index
CRP	C-reactive protein
CVD	Cardiovascular disease
DNL	De-novo lipogenesis
FMD	Flow-mediated dilation
GC	Gas chromatography
GLM	General Linear Model
HbA1c	Glycated hemoglobin
HDL	High-density lipoprotein
HOMA-IR	Homeostatic Model Assessment for Insulin Resistance
IQR	Interquartile range
ITT	Intention to treat
LDL	Low-density lipoprotein
MRI	Magnetic resonance imaging
NAFLD	Non-alcoholic fatty liver disease
OGTT	Oral glucose tolerance test
PNPLA3	Patatin-like phospholipase domain protein 3
PP	Per protocol
PUFA	Polyunsaturated fatty acid(s)
PWV	Pulse-wave velocity
SCD-1	Stearoyl coenzyme-A desaturase 1
SD	Standard deviation
T2D	Type 2 diabetes
UPLC-MS/MS	Ultra-high performance liquid chromatography coupled to tandem mass spectrometry

## 1. Introduction

Randomized controlled studies investigating the impact of replacing dietary carbohydrates with polyunsaturated fat (PUFA) on liver fat content and cardiometabolic risk in individuals with prediabetes and T2D are lacking. Also, the effects of a Healthy Nordic Diet on liver fat content and glycemic control have not been investigated. This study therefore aims to:

- Investigate the effects of the diets on liver fat content (primary aim)
- Investigate the effects of the diets on pancreatic fat, visceral fat, lean tissue, glycemic and lipid control
- Investigate the effects of the diets on plasma markers of de novo lipogenesis (DNL) and desaturation (i.e. stearoyl-Coenzyme desaturase 1, SCD-1) as well as on hepatic DNL using MRI spectroscopy
- Investigate gene-diet interactions, especially if common gene variants (e.g. in PNPLA3) known to increase liver fat and dyslipidemia, may modify the dietary effects.
- Perform lipidomic analyses to identify potential mechanistic pathways that may associate with diet-induced changes in liver fat, pancreatic fat, visceral fat, insulin sensitivity, dyslipidemia or DNL

Our hypothesis is that a customized diet will effectively reduce liver fat through suppression of hepatic DNL and SCD-1 activity, and thereby improve atherogenic dyslipidemia, insulin resistance and hyperglycemia in individuals with prediabetes and T2D.

## 2. Study design

**Study Type:** Interventional (Single-center Clinical Trial)

**Estimated Enrollment:** 150 participants

**Allocation:** Randomized

**Intervention Model:** Parallel assignment

**Intervention Model Description:** Parallel assignment

**Masking:** Double (Care Provider, Outcomes Assessors)

**Primary Purpose:** Treatment

**Hypothesis Testing Framework:** Superiority Trial

Eligibility criteria are presented below:

### **Inclusion criteria**

- Men and women
- 30-75 years
- BMI 25-40
- T2D (duration  $\leq$ 10 years, no insulin treatment) or prediabetes (ADA definition 2019) without diagnosed cardiovascular disease (CVD) during the last 2 years (e.g. myocardial infarction, stroke or angina pectoris)

### **Exclusion criteria**

- BMI  $>$ 40
- Alcohol intake  $>$ 20 g/day
- Unwillingness to follow a new prescribed diet for 1 year
- Diet-induced weight loss ( $\geq$ 10%) the preceding 3 months of screening
- Malignant disease
- Severe kidney and liver disease
- Heart failure or other severe CVD
- Claustrophobia or metal parts in the body (MRI)

Subjects enrolled in this study will be allocated to three different diet groups in a 1:1:1 allocation ratio using stratified randomization with type-2 diabetes status (yes/no) and gender (male/female) as stratifying factors. Subjects will be followed prospectively for 12 months.

The three diet-groups are:

**Experimental:** Customized diet to reduce liver fat

Ad libitum diet high in plant-derived PUFA and lower in carbohydrates

**Experimental:** Healthy Nordic diet

Ad libitum diet, based on Nordic foods, higher in carbohydrates (high fiber/low GI) and lower in fat but rich in monounsaturated fatty acids (MUFA) and PUFA

**Active Comparator:** Control

Ad libitum diet in accordance with the Nordic Nutrition Recommendations

Further details of each diet can be found in the study protocol registered at ClinicalTrials.gov (NCT04527965).

## **2.1. Sample size calculation**

The sample size calculation was based on Lehr's formula for comparison between two groups, assuming equal treatment effects for the two experimental diets. The standard deviation (SD) of the change in liver fat was 1.95 and 2.42 in two of our previous trials (1,2). As the population in the NAFLD trial will differ (e.g. higher prevalence of type 2 diabetes) compared to these other trials, we assume a SD of 3 for the current calculation. Given that 5% liver fat is the cut-off for NAFLD, we considered a 2% difference between groups as clinically relevant. To detect a difference of 2%-points in liver fat between the control group and one experimental group, n=36 individuals per group are needed with  $\beta=0.80$  and  $\alpha=0.05$ . To allow for 25% drop-out, n=50 individuals per group will be included. Thus, a total of n=150 individuals will be randomized.

## **3. Aims and objectives**

The overall aim of this study is to investigate the long-term impact of a customized diet aimed at reducing liver fat specifically and a healthy Nordic diet on ectopic fat (liver, pancreatic and visceral) and cardiometabolic risk in individuals with prediabetes and type 2 diabetes.

## **4. Outcomes**

### **4.1. Primary outcome**

- Between-group changes in liver fat content between baseline and month 12

[Time Frame: 12 months] [Unit: %] [Variable: Continuous]

Assessed by magnetic resonance imaging (MRI)

### **4.2. Secondary outcomes**

- Between-group changes in visceral adipose tissue mass between baseline and month 12

[Time Frame: 12 months] [Unit: L] [Variable: Continuous]

Assessed by magnetic resonance imaging (MRI)

- Between-group changes in lean tissue mass between baseline and month 12

[Time Frame: 12 months] [Unit: L] [Variable: Continuous]

Assessed by magnetic resonance imaging (MRI)

- Between-group changes in total body fat mass between baseline and month 12  
 [Time Frame: 12 months] [Unit: L] [Variable: Continuous]  
 Assessed by magnetic resonance imaging (MRI)
- Between-group changes in body weight between baseline and month 12  
 [Time Frame: 12 months] [Unit: kg] [Variable: Continuous]  
 Assessed by using a Tanita bioelectrical impedance analysis (BIA) scale
- Between-group changes in glycated hemoglobin (HbA1c) between baseline and month 12  
 [Time Frame: 12 months] [Unit: mmol/mol] [Variable: Continuous]  
 Assessed by routine clinical chemistry
- Between-group changes in Homeostatic Model Assessment for Insulin Resistance (HOMA-IR) between baseline and month 12  
 [Time Frame: 12 months] [Unit: none] [Variable: Continuous]  
 Calculated by multiplying fasting plasma glucose (mmol/L) with fasting serum insulin (mU/L) and dividing the product by 22.5.  
 Assessed by routine clinical chemistry
- Between-group changes in fasting plasma glucose between baseline and month 12  
 [Time Frame: 12 months] [Unit: mmol/L] [Variable: Continuous]  
 Assessed by routine clinical chemistry
- Between-group changes in fasting serum insulin between baseline and month 12  
 [Time Frame: 12 months] [Unit: mU/L] [Variable: Continuous]

Assessed by routine clinical chemistry

- Between-group changes in systolic blood pressure between baseline and month 12

[Time Frame: 12 months] [Unit: mmHg] [Variable: Continuous]

Assessed by using an automated blood pressure monitor

- Between-group changes in diastolic blood pressure between baseline and month 12

[Time Frame: 12 months] [Unit: mmHg] [Variable: Continuous]

Assessed by using an automated blood pressure monitor

- Between-group changes in plasma lipids (total cholesterol, LDL cholesterol, triglycerides, HDL cholesterol, apoB and apoA1) between baseline and month 12

[Time Frame: 12 months] [Unit: mmol/L or g/L (apoB and apoA1)] [Variable: Continuous]

Assessed by routine clinical chemistry

- Between-group changes in circulating inflammatory markers (CRP, Tumor Necrosis Factor Alpha-receptor 1 and 2, Interleukin-1 receptor antagonist, Fibroblast growth factor 21) between baseline and month 12

[Time Frame: 12 months] [Unit: ng/l or mg/l (CRP)] [Variable: Continuous]

Assessed by routine clinical chemistry and ELISA

- Between-group changes in pancreatic fat between baseline and month 12

[Time Frame: 12 months] [Unit: %] [Variable: Continuous]

Assessed by magnetic resonance imaging (MRI)

- Between-group changes in flow-mediated dilation (FMD) between baseline and month 12

[Time Frame: 12 months] [Unit: %] [Variable: Continuous]

Assessed by ultrasound in approximately half of the study population (n=75)

- Between-group changes in pulse-wave velocity (PWV) between baseline and month 12  
[Time Frame: 12 months] [Unit: m/s] [Variable: Continuous]

Assessed by ultrasound in approximately half of the study population (n=75)

- Between-group values in FMD and PWV at month 12  
[Unit: % and m/s] [Variable: Continuous]

Assessed by ultrasound in the whole population (n=150)

- Between-group changes in liver fat, HbA1c, and blood lipids in prespecified subgroups of type-2 diabetes status (yes/no), gender (male/female), individuals with NAFLD/without NAFLD at baseline, individuals with the CC vs CG/GG I148M genotype in PNPLA3, and in individuals with low respectively high dietary compliance based on dietary and lipogenic biomarkers changes (e.g. linoleic acid, DHA and palmitoleic acid changes from baseline to 12 months) between baseline and month 12

[Time Frame: 12 months]

We will assess whether response to diets in liver fat, HbA1c and blood lipids differ between gender, high vs low compliers, genotype, individuals with prediabetes or diabetes or those who have NAFLD/do not have NAFLD at baseline

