### **5. Populations and subgroups to be analyzed**

#### **5.1 Populations**

**Intention to treat (ITT):** All subjects randomized at baseline will constitute the ITT-population and will be the primary study population for the analyses. Missing data will be imputed as described in section 7 in this document.

**Per-protocol (PP):** All subjects completing the study period with complete data on the outcome of interest will constitute the PP-population. The PP-population will be the secondary study population for the analyses.

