## **6.2 Secondary and exploratory outcomes**

For secondary and exploratory outcomes GLMs will be applied using  $\Delta$ values between baseline and month 12 for each continuous variable (see point 4.2 and 4.3) as dependent variables and type-2 diabetes status (yes/no), gender (male/female) and baseline outcome values as included covariates in the model. Outcome values from 6 months follow-up will be presented descriptively.

The GLM will be applied for the ITT-population (defined above) as well as for the PP-population (defined above) for HbA1c, LDL cholesterol, triglycerides and systolic- and diastolic blood pressure. For the remaining secondary and exploratory outcomes, a PP-population will be used. Independent samples post-hoc t-tests will follow if between-group statistical significance is observed.

Treatment effects will be presented as mean or median differences (%) with 95% confidence intervals and with corresponding p-values.

When assumptions of the GLM are not satisfied, the Willett's residual method will be applied (3), followed by Mann-Whitney U post-hoc tests.

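### The change-from-baseline model in SAP section 6.2 does not fit the month-12 FMD and PWV outcome in the whole population, because only about half appear to have a baseline scan

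*SAP*

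**What the plan says.** SAP section 4.2 lists FMD change and PWV change as two secondary outcomes, each with the note "Assessed by ultrasound in approximately half of the study population (n=75". A further secondary outcome follows, "Between-group values in FMD and PWV at month 12", with the note "Assessed by ultrasound in the whole population (n=150". It is tagged as continuous.

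Section 6.2 sets one model for the secondary and exploratory outcomes. It uses "values between baseline and month 12 for each continuous variable (see point 4.2 and 4.3) as dependent variables", and it names diabetes status, gender and "baseline outcome values as included covariates in the model". The month-12 outcome is not excepted.

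On the analysis population, section 6.2 names five outcomes for analysis in both the ITT and the PP population; FMD and PWV are not among them. It then says: "For the remaining secondary and exploratory outcomes, a PP-population will be used". Section 5.1 defines that population: "All subjects completing the study period with complete data on the outcome of interest will constitute the PP-population". Imputation is introduced in section 5.1 under the ITT population: "Missing data will be imputed as described in section 7 in this document". Section 7 itself names no population and covers explanatory as well as dependent variables.

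**The concern.** A change score needs a baseline value, and so does a baseline covariate. The month-12 outcome is defined for everyone, but the sample sizes in section 4.2 imply that about half have no baseline ultrasound. The only model the SAP provides for this outcome therefore cannot be fitted in the population for which the outcome is defined. In the participants where it can be fitted, it is the same analysis as the FMD and PWV change outcomes.

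The analyst must then choose a model that the SAP does not state, possibly after seeing the data. The obvious choice, comparing month-12 values with no baseline term, keeps everyone but makes no use of the baseline scans that were collected. The stakes are the precision and the prespecification of two secondary vascular measures. The primary liver-fat analysis is not affected.

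**Working it through.** **The plan's own figures.** Section 2.1 gives no power figure for FMD or PWV. Its liver-fat figure reproduces: Lehr's formula gives 16 × 3² / 2² = 36 per group. Allowing for 25% drop-out gives 36 / 0.75 = 48, which the plan takes up to 50 per group, 150 in total. Only the 50 per group and the 25% are used below.

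**Who can enter the section 6.2 model.** Change is available for about 75 and month-12 values for 150, in three equal arms. That is about 25 per arm with baseline, out of 50. That the other half lack a baseline scan is inferred from these two numbers; the SAP does not say it outright.

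**Upper limit of the loss.** If baseline told us nothing about month 12 (r = 0), using 25 instead of 50 per arm would change the standard error of a two-arm difference from √(2/50) = 0.200 SD to √(2/25) = 0.283 SD, a ratio of √2 = 1.41. The difference detectable with 80% power at two-sided 0.05 would go from 2.80 × 0.200 = 0.56 SD to 2.80 × 0.283 = 0.79 SD. (The SAP gives 0.05 without stating sidedness.)

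**Allowing for r.** Adjusting for baseline multiplies the variance by (1 − r²). With 25 per arm the standard error is 0.283 × √(1 − r²): 0.245 SD at r = 0.5 and 0.200 SD at r = 0.71. At the latter value it equals the unadjusted whole-population analysis, and above it the half-sample analysis is the more precise.

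**With 25% drop-out.** Completers per arm: 50 × 0.75 = 37.5, of whom 18.75 have baseline. Effective completers per arm, on the scale of an unadjusted month-12 comparison:

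- A, section 6.2 model in the half with baseline: 18.75 / (1 − r²)
- B, month-12 value in all, no baseline term: 37.5
- C, constrained longitudinal model with a common baseline mean: 18.75 / (1 − r²) + 18.75
- D, mean fill with a missing-baseline indicator. Least squares weights both halves equally, so the average residual variance is (1 − r²/2) times the unadjusted one: 37.5 / (1 − r²/2)

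| r (assumed) | A | B | C | D | C over B | D over B |
|---|---|---|---|---|---|---|
| 0.4 | 22.3 | 37.5 | 41.1 | 40.8 | 10% | 9% |
| 0.5 | 25.0 | 37.5 | 43.8 | 42.9 | 17% | 14% |
| 0.6 | 29.3 | 37.5 | 48.0 | 45.7 | 28% | 22% |
| 0.7 | 36.8 | 37.5 | 55.5 | 49.7 | 48% | 32% |

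Across this range A runs from 22.3 / 37.5 = 60% of B to 36.8 / 37.5 = 98% of B. Both C and D exceed A and B in every row.

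**The case against.** **A sensible analyst would not discard the data.** A reader might infer that the SAP instructs the team to throw away half the month-12 scans. The document does not support that. Section 4.2 defines this outcome as a value, gives its sample as everyone, and lists the change outcomes separately. The natural course is to compare month-12 values in all. The PP definition does not itself demand a baseline scan either: if the outcome of interest is the month-12 value, every completer with that scan qualifies. What stands is narrower. The change-score and baseline-covariate clauses of section 6.2 do not fit this outcome, and no other model is given.

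**Imputation might fill the gap.** Section 7 covers explanatory variables and names no population, so it could be read as filling in the missing baselines. But section 5.1 introduces imputation under ITT, and section 6.2 sends FMD and PWV to the PP population, which rests on complete outcome data. Section 7 does not clearly resolve the problem.

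**Two estimates are not a contradiction.** A reader might also infer that each measure gets two competing answers and that one must be declared the winner. The SAP does not rank its secondary outcomes. A change analysis in a subset and a month-12 comparison in everyone are two separately listed outcomes that can both be reported. There is no need to reduce the change outcomes to descriptive status.

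**The loss may be small.** This is correct if r is near 0.7, and r is not in the SAP.

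**Conclusion.** The concern holds as a mismatch between a listed outcome and the only model offered for it. Taken literally, section 6.2 can use about 75 of 150 participants for the month-12 FMD and PWV outcome and duplicates the change outcomes. Relative to a month-12 comparison without baseline, the literal reading costs about 40% of effective sample size at r = 0.4 and about 2% at r = 0.7. Using all month-12 values together with the available baselines gains about 10-48% (longitudinal model) or 9-32% (mean fill with indicator) over that comparison.

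These figures rest on several assumptions: the 25% drop-out allowance applies equally to both halves; the half with baseline is spread evenly over the arms and its selection is unrelated to outcome; the outcome SD is equal in both halves; and r lies between 0.4 and 0.7. Only the drop-out allowance itself comes from the SAP. The consequence is confined to two secondary measures.

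**What to change.** Add a rule to section 6.2 for the month-12 FMD and PWV outcome:

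- dependent variable: the month-12 value;
- diet group as factor, diabetes status and gender as covariates;
- population: all completers with a month-12 measurement;
- baseline FMD or PWV used where it was measured, by one method named in advance: either a constrained longitudinal model with a common baseline mean across arms, or a baseline covariate with mean fill and a missing-baseline indicator;
- a statement that this rule, and not section 7, governs baselines that were not measured.

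Keep the FMD and PWV change analyses in the half with baseline as the secondary outcomes they are now.

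The cost is a few sentences of SAP text and a slightly more complex model for two secondary measures, with no extra measurements. Of the two methods, the longitudinal model is the more efficient and mean fill with an indicator is the simpler to fit. A month-12 model with no baseline term would also remove the mismatch, but would forgo the gain shown above.

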#### 4.3. Exploratory outcomes

- Between-group changes in plasma and imaging-derived fatty acids and fatty acid ratios in the lipogenic pathway (i.e.16:1n-7, 18:1n-9, 16:0, 14:0, 18:0 and 16:1n-7/16:0, 16:0/18:2n-6, 16:1n-7/18:2n-6) between baseline and month 12

[Time Frame: 12 months] [Unit: %] [Variable: Continuous]

Fatty acids are measured as percentage change of all fatty acids, thus using one unit for the above five fatty acids. Assessed by gas chromatography (GC) and proton spectroscopy, and use of bioinformatic modelling (untargeted) to identify responders and non-responders in liver fat reduction and improvement in glycemic control and blood lipids (i.e. personalized medicine approach)

- Between-group changes in plasma lipids (ceramides) using a targeted lipidomic approach between baseline and month 12

[Time Frame: 12 months] [Unit: absolute and relative amounts] [Variable: Continuous]

Lipids are measured using ultra-high performance liquid chromatography coupled to tandem mass spectrometry (UPLC-MS/MS)

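### SAP 4.3: with one diet and one change per person, individual responders to diet are not identifiable; the aim should be restated as effect modification by baseline markers against control

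*SAP*

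**What the plan says.** - **Objective.** SAP section 4.3, inside the first exploratory outcome (fatty acids and their ratios), announces an untargeted bioinformatic model "to identify responders and non-responders in liver fat reduction and improvement in glycemic control and blood lipids (i.e. personalized medicine approach".
- **Design.** Section 2 gives "Intervention Model: Parallel assignment". Participants are "allocated to three different diet groups in a 1:1:1 allocation ratio", and "Subjects will be followed prospectively for 12 months" (both in section 2, below the exclusion criteria). There is no crossover and no repeat exposure.
- **Outcome per person.** The primary outcome is "Between-group changes in liver fat content between baseline and month 12", and sections 4.2 and 4.3 follow the same pattern. For secondary and exploratory outcomes, section 6.2 adds: "Outcome values from 6 months follow-up will be presented descriptively".
- **Analysis.** Sections 6.1 and 6.2 give linear models of the change, adjusted for diabetes status, gender and baseline value, with no interaction term. Section 6.3 gives correlations between changes. None of them describes the responder modelling. The SAP states no label rule, predictors, control comparison or validation for it.

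**The concern.** A person responds to a diet if the outcome on that diet differs from what the same person would have had on control. Only one of the two is ever observed here. The observed change also contains a year of natural course, measurement error, regression to the mean and co-interventions, which section 4.5 expects and records.

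If people are sorted by how far they fell, the labels describe who changed, not who changed because of the diet. Such labels would appear in every arm, control included, and would appear even if the diet worked equally in everyone. A marker that predicts change on any diet would then be reported as a marker of diet response. At stake is a misleading personalised-medicine claim from this trial.

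**Working it through.** **Inputs from SAP 2.1.** SD of change in liver fat: 3 assumed ("we assume a SD of 3 for the current calculation"), 1.95 and 2.42 in two earlier trials. Relevant between-group difference: 2 percentage points. Needed: 36 per group; planned: 50 per group.

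**Assumptions of this check.** Normal changes; zero mean change without diet effect unless stated; responder cut either any reduction or a 2-point reduction. The SAP gives no cut, and its 2 points are a difference between groups, not a threshold for a person.

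**1. The plan's own figure.** Lehr's formula: 16 × (3/2)² = 36 per group, as stated. With 25% drop-out, 36/0.75 = 48, against 50 planned. The inputs are used consistently.

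**2. What is identifiable.** Write change = course without the diet + effect of the diet + error. One value per person gives only the sum. Randomisation identifies the mean diet effect, and the mean diet effect at each level of a baseline marker. It does not identify each person's effect. A month-6 value is taken on the same diet, so it supplies no second exposure.

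**3. No diet effect, 2-point cut.** Share labelled responder = Φ(−2/SD):
- SD 3: Φ(−0.667) = 0.252
- SD 2.42: Φ(−0.826) = 0.204
- SD 1.95: Φ(−1.026) = 0.153

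**4. Identical 2-point benefit in everyone, SD 3.**

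| Cut | Diet arm: non-responders | Control: responders |
|---|---|---|
| Any reduction | 1 − Φ(2/3) = 25% | Φ(0) = 50% |
| 2-point reduction | 1 − Φ(0) = 50% | Φ(−2/3) = 25% |

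With the any-reduction cut, the diet-arm figure is 20% at SD 2.42 and 15% at SD 1.95. If the control mean change were −1 (SD 3, any reduction), Φ(1/3) = 63% of controls and Φ(3/3) = 84% of the diet arm would be labelled responders.

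**5. A purely prognostic marker.** Simulation: 4,000 runs, 50 per arm, SD 3, effect −2 in everyone, marker correlated 0.4 (assumed) with change in both arms, no interaction. Splitting the diet arm at −2 and comparing the marker between the two labels gave p<0.05 in 64% of runs. A marker-by-diet test against control gave p<0.05 in 4.9%, its nominal rate.

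**6. Would comparing the SD of change between arms settle it?** With a two-sided 5% F-test, 80% power needs a variance ratio of about 2.25 at 50 per arm, or 2.62 at 36. If individual effects add independently to a control SD of 3, their SD must be 3 × √(2.25 − 1) = 3.35 or 3 × √(2.62 − 1) = 3.82. Either exceeds the total SD the SAP assumes.

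**7. Precision of an interaction.** For a binary marker split evenly, and ignoring the gain from baseline adjustment, SE = 3 × √(4/(n/2)). At n = 50 per arm this is 3 × √(4/25) = 1.20, so the 95% half-width is 1.96 × 1.20 = 2.4 points. At n = 36 it is 3 × √(4/18) = 1.41, half-width 2.8 points.

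**The case against.** The strongest reply is that section 4.3 names no method. It sets no cut, does not say that arms are classified separately, and lists no predictors; a marker-by-diet model would also fit its words. This stands. That people will be sorted by observed change is an inference from the stated target, not something the SAP commits to.

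A second reply is that the SAP already asks about effect modification. Section 1 names gene-diet interactions, and sections 4.2 and 5.2 prespecify subgroups for liver fat, HbA1c and blood lipids. This stands in part: the group-level question is raised. But section 5.2 runs the subgroups with the full-population models, which have no interaction term, and nothing links them to the untargeted modelling. Baseline adjustment in sections 6.1 and 6.2 helps with regression to the mean in the specified models, but does not extend to a responder label the SAP leaves undefined.

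A third reply is that the illustration depends on chosen cuts. This also stands. The 50% figure arises because the cut sits at the mean of a symmetric distribution; with any reduction as the cut it is 25%. Neither is an estimate of what the trial will produce.

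A reader might infer that a parallel trial cannot address personalised diet effects at all. The documents do not support that: three randomised arms with a control allow differences in effect by baseline marker to be estimated. What they cannot deliver is a label for an individual.

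**Conclusion.** The point holds in a limited form. Individual response to diet is not identifiable from one diet and one baseline-to-month-12 change per person, and no other section of the SAP repairs this. On the most natural reading of section 4.3, and under the assumptions stated, 15% to 25% of an arm would be called responders with no diet effect (2-point cut). At SD 3, 25% to 50% of a diet arm would be called non-responders although everyone benefits equally. The conclusion rests on the design; the percentages only show its possible size.

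Severity is low. A reader might take this as a threat to the trial's main result, but the clause is exploratory and affects neither the sample size nor any primary or secondary estimate.

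**What to change.** Restate the section 4.3 objective as exploratory effect modification by baseline markers. Model the change on baseline value, randomised diet, baseline markers and marker-by-diet terms, with control as reference, and report cross-validated performance for the predicted diet-versus-control difference. If the team prefers to model observed change, call it prediction of observed change and drop the responder and personalised-medicine wording.

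Any comparison of the SD of change between arms should be descriptive only. Given step 6 above, absence of excess SD must not be read as absence of heterogeneity.

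The cost is SAP wording and a different specification for an analysis already planned; no new data are needed. The downside is precision: with about 36 to 50 per arm, interaction estimates will be wide (step 7), and an inconclusive result is likely unless effects differ strongly.
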